2.2.2. Vibegron

Vibegron is a potent, highly selective, orally available, β_3 -AR agonist demonstrating > 9000-fold selectivity for activation of β_3 -AR over β_2 -AR and β_1 -AR in cell-based in vitro assays.

Nonclinical and clinical studies suggest β_3 -AR activation is a novel target for treating pain and gastrointestinal motility in patients with IBS. β_3 -ARs are widely expressed and distributed on vascular and non-vascular smooth muscle and enteric neurons in the gastrointestinal tracts of many species, including humans [Cellek, 2007; De Ponti, 1996; Anthony, 1996; Krief, 1993].

Mechanistically, β_3 -AR agonists are hypothesized to reduce colon smooth muscle contractions, enteric neuron hyperactivity, and visceral pain by mediating a direct effect on smooth muscle and indirectly by promoting release of somatostatin within the intestine. In isolated circular muscle strips of human colon, activation of β_3 -AR induced smooth muscle relaxation [Cellek, 2007; De Ponti, 1999; Bardou, 1998; De Ponti, 1996], which was blocked using β_3 -AR antagonists [Schemann, 2010; De Ponti, 1999]. In addition, β_3 -AR agonists have been shown to reduce hyperexcitability of human enteric neurons and stimulate release of somatostatin [Schemann, 2010; Cellek, 2007], which inhibits submucosal neuronal excitability and pain in both animal models and humans [Prasoon, 2015; Shi, 2014; Mihara, 1987].

Approximately 2300 subjects (including 1840 with overactive bladder and 460 healthy subjects) have received vibegron in 19 clinical studies. Data from these studies indicate that vibegron has been well tolerated when administered alone or in combination with the following drugs: antimuscarinics (imidafenacin or tolterodine); metoprolol (a representative beta-blocker); or amlodipine (a representative vasodilator). Assessment of safety laboratory parameters and mean vital sign values over time, including heart rate and blood pressure, showed no clinically meaningful differences for any active treatment group relative to placebo or an antimuscarinic comparator. Discontinuation rates due to AEs were low (less than 5%) in all clinical studies. A more detailed description of vibegron, including pharmacology, efficacy, and safety data in overactive bladder, is provided in the most recent version of the Investigator's Brochure.

2.3. Benefit/Risk Assessment

2.3.1. Potential Benefits

Vibegron's novel mechanism of action has the potential to demonstrate significant therapeutic benefit in subjects with IBS pain. Early phase clinical studies of another β_3 -AR agonist, solabegron, showed improvement in the pain scores of women with IBS and no effect on gut motility in healthy subjects [Grudell, 2008; Kelleher, 2008].

2.3.2. Potential Risks

To date, in subjects (male or female) with overactive bladder, no adverse reactions specific to vibegron have been identified.

Based on aggregate preclinical, clinical pharmacology, and Phase 2 and 3 studies, AEs of special interest (AESIs) predefined for specific evaluations in vibegron clinical studies are as follows:

[figure not shown]
- Potential major cardiovascular events
- Hypertension
- AEs suggestive of orthostatic hypotension
- AEs suggestive of cystitis or urinary tract infection
- Elevated AST or ALT lab value requiring that the study drug be temporarily withheld or permanently discontinued

Prespecified definitions of AESIs are provided in [Section 8.4.7](#). More detailed information about the known and expected benefits and risks and reasonably expected AEs of vibegron may be found in the most recent version of the Investigator's Brochure.

3. Objectives and Endpoints

Objectives	Endpoints
Primary	
To compare the effect of vibegron vs placebo in subjects with abdominal pain due to IBS-D on the API weekly responder rate over 12 weeks
 
 • Proportion of IBS-D subjects who are API weekly responders over 12 weeks 
 - An API Weekly Responder is defined as a subject who experiences a decrease in the weekly average of “worst abdominal pain in the past 24 hours” scores of at least 30% compared with the baseline weekly average
Secondary	
To compare the effect of vibegron vs placebo in subjects with abdominal pain due to IBS-D or IBS-M on patient-reported outcomes
 
 • Proportion of GIS responders at Week 12 for all IBS subjects, including IBS-D and IBS-M subjects

To compare the effect of vibegron vs placebo in subjects with abdominal pain due to IBS-D on the API weekly responder rate over 12 weeks based on different thresholds of improvement
	
 • Proportion of IBS-D subjects who are API weekly responders over 12 weeks 
 - An API Weekly Responder is defined as a subject who experiences a decrease in the weekly average of “worst abdominal pain in the past 24 hours” scores of at least 40% compared with the baseline weekly average • Proportion of IBS-D subjects who are API weekly responders over 12 weeks 
 - An API Weekly Responder is defined as a subject who experiences a decrease in the weekly average of “worst abdominal pain in the past 24 hours” scores of at least 50% compared with the baseline weekly average

To compare the effect of vibegron vs placebo in subjects with abdominal pain due to IBS-D or IBS-M on safety endpoints
	
 • AEs, clinical laboratory values, vital signs

Objectives	Endpoints
Other/Exploratory	

Objectives	Endpoints

Objectives	Endpoints

AE(s) = adverse event(s); API = Abdominal Pain Intensity; GIS = Global Improvement Scale; IBS = irritable bowel syndrome; IBS-D = irritable bowel syndrome with predominantly diarrhea; IBS-M = irritable bowel syndrome with mixed episodes of diarrhea and constipation; PRO = patient-reported outcomes; IBS-QoL = irritable bowel syndrome Quality of Life; WPAI = Work Productivity and Activity Impairment

4. Study Design

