9.4.3. Safety Analyses

The safety analysis will be performed using the Safety Analysis Set and will be fully defined in the SAP. The safety parameters will include AEs and clinical laboratory and vital sign parameters. For each safety parameter of the clinical laboratory and vital sign parameters, the last non--missing safety assessment before the first dose of double-blind study drug will be used as the baseline for all analyses of that safety parameter.

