9.4.3.3. Vital Signs

Descriptive statistics of observed values and change from baseline for vital signs will be presented for each treatment group by visit.

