4.2.2. Reporting Conventions

General rules

In general, all collected safety data and any derived efficacy parameters from daily evening pain diary and daily bowel movement diary and PRO data will be presented in subject data listings, for all enrolled subjects. Listings will be ordered by treatment subject number, and assessment week or event date. The treatment group presented in listings will be based on the planned assignment, unless otherwise noted.

Summary tables will be provided for all randomized subjects. All demographic and baseline data will be presented by treatment arm and overall, unless otherwise specified. Efficacy, PRO and safety data will be presented by treatment arm only. In general, continuous variables will be summarized to include the population sample size (N), number of subjects with available data (n), arithmetic mean, SD, median, minimum, Q1, Q3 and maximum values. Categorical variables will be summarized by the population size (N), number of subjects with available data (n), number of subjects in each category, and the percentage of subjects in each category. Unless otherwise noted, the denominator to determine the percentage of subjects in each category will be based on the number of subjects with available data (n) in the analysis set of interest. Selective ordinal data may be summarized using both descriptive statistics and counts and percentages of subjects in each category, as appropriate.

The data analyses will be conducted using the SAS® System (SAS Institute Inc., Cary, NC) version 9.4 or above. The [REDACTED]’ standard operating procedures will be followed for the validation of all SAS programs and outputs.

Formats

Numeric data will be reported at the precision collected on the eCRF. The reported precision from non eCRF sources may be adjusted to a clinically interpretable number or decimal places.

Unscheduled Visits

Unscheduled visits will be assigned to a study visit using the all-inclusive windows defined in [Section 4.2.4](#). However, for by visit summaries, only the planned assessment time points will be summarized. Assessments at unscheduled visits will be included for “any time On-treatment” timepoints and in data listings, as well as algorithms to determine the maximum.

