7. SAFETY ANALYSIS

The SAF will be used for all safety analyses. Safety will be assessed on the basis of extent of exposure and compliance, AE reports, clinical laboratory data, ECGs, physical examinations, and vital signs.

No inferential statistical testing is planned on the safety data, all data will be descriptively summarized by treatment and visit.

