7.5. Vital Signs

Vital sign data including blood pressure, pulse rate and body temperature will be collected at all study visits except for the safety telephone follow-up visit. Body weight will be measured at Screening, baseline visit and Week 12 and Height will be measured at Screening only. Blood pressure and pulse will be measured in triplicate at each visit. The average of triplicates will be used for summary.

For all parameters, absolute values and change from baseline will be presented for scheduled visits using descriptive statistics for continuous variables. In addition, the maximum post-baseline, change from baseline to the maximum post-baseline, and change from baseline to the end of treatment will be summarized for each of the vital signs.

To further investigate changes in SBP/DBP/pulse rate from baseline, the following tables will be prepared:

- Counts and percent of subjects in each group with at least a 5/10/15 CFB at 3 consecutive post-baseline visits and at Week 12 will be produced for all subjects, by pre-existing hypertension category (Yes/No) and by baseline hypertension category (Yes/No). If the percentage of subjects in a subgroup is less than 25% of the total population, the subgroup in question will be not included in summary
- CFB in Maximum post-baseline (including 95% CI of Mean)

A by-subject listing, sorted by subject identifier, will be presented including all vital sign results (scheduled or unscheduled).

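### The secondary safety objective is a comparison with placebo, but the plan reports no between-arm estimate for any safety endpoint; a baseline-adjusted difference for blood pressure and pulse would be a cheap improvement

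*Protocol*

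**What the plan says.** Protocol Section 3 and SAP 1.1.2 list as a secondary objective "To compare the effect of vibegron vs placebo in subjects with abdominal pain due to IBS-D or IBS-M on safety endpoints". The endpoints are "AEs, clinical laboratory values, vital signs". Protocol 9.4.3 leaves the detail to the SAP: "The safety analysis will be performed using the Safety Analysis Set and will be fully defined in the SAP".

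The analyses then specified are:

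- **Protocol 9.4.3.3:** "Descriptive statistics of observed values and change from baseline for vital signs will be presented for each treatment group by visit".
- **SAP 7:** "No inferential statistical testing is planned on the safety data, all data will be descriptively summarized by treatment and visit".
- **SAP 7.3:** counts and percentages of subjects with TEAEs. One table is restricted to preferred terms reaching 2% on vibegron and exceeding placebo. Hypertension TEAEs are also split by pre-existing and by baseline hypertension.
- **SAP 7.4:** laboratory values, changes and shift tables by arm.
- **SAP 7.5:** observed values and changes by visit; counts of subjects with a change of at least 5, 10 or 15 in systolic pressure, diastolic pressure or pulse, overall and by hypertension category; and "CFB in Maximum post-baseline (including 95% CI of Mean").

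None of the safety tables in SAP 11.1.1 or safety figures in SAP 11.1.2 is described as containing a difference in means, a risk difference, a ratio or an interval for a contrast between arms.

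**The concern.** An objective that promises a comparison with placebo should lead to a planned estimate of the difference and its uncertainty. The plan does this for efficacy. SAP 6.1.1 gives the primary endpoint a stratified risk difference with a 90% CI, although SAP 4.1.2 calls all efficacy analyses descriptive. So the descriptive status of the safety analysis does not by itself explain why the contrast is missing.

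Blood pressure and pulse are where this matters most. Hypertension is an AESI (protocol 2.3.2, SAP 7.3), and SAP 7.5 sets out extra tables to look further at these parameters. All of the roughly 200 randomized women who take double-blind drug contribute to safety, against about 90 evaluable IBS-D women for the primary endpoint. The trial's more precise information on vibegron versus placebo would be reported without its most useful summary.

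**Working it through.** **Figures in the plan.** No numerical target or precision is stated for safety, so there is no safety figure to reproduce. The one related figure is the power statement in protocol 9.2. With 45 per arm, 51% versus 31% and two-sided alpha 0.10, the pooled-variance formula gives (0.20 − 1.645 × √(2 × 0.41 × 0.59/45)) / √((0.51 × 0.49 + 0.31 × 0.69)/45) = 0.29, a power of 61.4% against the stated 60% or so. The sample-size inputs are read correctly, but the point does not depend on them.

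**What the planned safety interval measures.** It concerns each woman's largest post-baseline value minus baseline. There are four scheduled post-baseline visits (Weeks 2, 4, 8 and 12, protocol 1.3), and SAP 4.2.2 also lets unscheduled readings enter the maximum. Assume normal readings with equal variance, equal correlation and no drug effect. The expected maximum of four independent standard normals is 1.03, and the within-woman SD is the SD of change divided by √2. The expected mean change to the maximum is then 1.03 × SD/√2:

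- SD 8 mmHg: 5.8 mmHg
- SD 12 mmHg: 8.7 mmHg

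A rise of that order would be expected on placebo too, so the interval informs the objective only when set against the other arm.

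**What can be derived by hand.** SAP 4.2.2 requires n, mean and SD for continuous variables, and counts with percentages for categories. For change at any visit, the difference in means ± 1.96 × √(SD₁²/n₁ + SD₂²/n₂) follows directly. With equal SDs and n per arm, the 95% half-width is 1.96 × SD × √(2/n):

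| SD of change (assumed) | n = 100 per arm | n = 90 per arm |
|---|---|---|
| 8 mmHg | 2.22 | 2.34 |
| 10 mmHg | 2.77 | 2.92 |
| 12 mmHg | 3.33 | 3.51 |

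The 90 per arm allows for the 10% discontinuation assumed in protocol 9.2.

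**What cannot be derived.** A baseline-adjusted difference needs the within-woman relation between baseline and follow-up, which the by-arm summaries do not show. With equal variances, the adjusted standard error is √((1 + ρ)/2) times that of the change score. For ρ = 0.5 the factor is 0.866 (13% shorter). For ρ = 0.7 it is 0.922 (8% shorter). The half-widths above would become about 1.9 (2.22 × 0.866) to 3.2 mmHg (3.51 × 0.922).

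**Adverse events, for illustration.** With assumed rates of 10% versus 5% and 100 per arm, the standard error is √(0.10 × 0.90/100 + 0.05 × 0.95/100) = 0.0371. The 95% interval is 5 ± 7.3 points, or −2.3 to 12.3. It too can be computed from the planned counts.

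**The case against.** The strongest reply is that the plan makes an explicit and common Phase 2 choice. SAP 7 rules out inferential testing on safety, the trial has no formal hypothesis even for efficacy, and nothing defines the word compare as a modelled contrast. Side-by-side summaries of randomized arms are a comparison of a kind. This stands as far as it goes, and it is why the gap is modest. It does not remove the gap: a descriptive difference with an interval is compatible with a no-testing statement, as the efficacy analyses show.

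A reader might go further and infer that the trial cannot yield a difference from placebo, that it sets no upper bound on a blood pressure effect, or that effects can only be judged by eye from two means or from whether intervals overlap. The documents do not support this. The planned statistics allow an unadjusted difference and its bound. Threshold counts and hypertension subgroup tables are planned alongside the means. No rule based on overlapping intervals appears anywhere.

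Two further cautions stand. That the 95% CI is within arm is an inference, since SAP 7.5 does not say so and table layouts are in a separate document (SAP 11.2). The sentence "Efficacy, PRO and safety data will be presented by treatment arm only" does not settle it: it covers efficacy as well, which does get differences, so it probably means only that there is no overall column. Also, the background statement in protocol 2.2.2 that earlier data "showed no clinically meaningful differences for any active treatment group relative to placebo or an antimuscarinic comparator" describes mean values over time. It does not show that earlier trials reported a modelled contrast.

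**Conclusion.** The concern holds as a mismatch between the stated objective and the reported output. The plan specifies no between-arm safety estimate, and its only safety interval, apparently within arm, is for a quantity that tends to be positive without any drug effect. What is lost is a reported difference with its interval and any baseline-adjusted version. Data collection and the primary result are not affected.

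The size is moderate: an unadjusted systolic difference would have a 95% half-width of about 2.2 to 3.5 mmHg, and adjustment would gain a further 8% to 13%. These figures rest on an assumed SD of change of 8 to 12 mmHg, 90 to 100 women per arm, and an assumed baseline-to-follow-up correlation of 0.5 to 0.7. The documents give no SD or correlation. This is an inexpensive improvement, not a flaw that undermines the trial.

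**What to change.** In SAP 7.5, add the baseline-adjusted vibegron-minus-placebo difference with 95% CI at Weeks 2, 4, 8 and 12 for systolic pressure, diastolic pressure and pulse. Use the MMRM terms in protocol 9.4.2.1 (treatment, visit, baseline, treatment by visit). Label the results descriptive and give no p-values, so that the no-testing statement in SAP 7 can stand. State the 95% level explicitly, because the protocol 9.4.2 default is 90%.

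Optionally, add to Table 14.3.2.1 risk differences with 95% CI for any TEAE, serious TEAE, TEAE leading to discontinuation and each AESI category. Name an interval method suited to sparse or zero counts; the simple normal interval used above for illustration is not.

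The cost is SAP wording and some extra table columns. No new data are needed, and the model form is already specified for efficacy. The downside is 3 × 4 = 12 vital-sign intervals plus 8 for adverse events (three overall categories and the five AESI categories in SAP 7.3), about 20 in all without multiplicity adjustment. The SAP should say so, so that no single interval is read as a test.

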4.1. Overall Design

This study is a Phase 2 randomized, double-blind, placebo-controlled, parallel-group, multicenter study to evaluate the efficacy and safety of vibegron in women with IBS-D or IBS-M. Subjects who meet all eligibility criteria will be randomized in a 1:1 ratio to receive either vibegron 75 mg or matched placebo. Randomization will be stratified by baseline abdominal pain intensity score (< 6 vs \geq 6 on a 0 to 10 numeric rating scale [NRS]) and IBS subtype (IBS-D vs IBS-M).

Enrollment for subjects with IBS-M will be capped at 50% of the total subject population (ie, up to 50% of the study population will be subjects with IBS-M). Stratification will be performed via central randomization across the study (not per site).

A Data Safety Monitoring Board (DSMB) will be retained to assess, on an ongoing basis, all safety aspects of this study, including SAEs, major adverse cardiac events (MACE), adverse events of special interest (AESIs), and all other AEs. The committee will meet to review the safety data at the following 3 times when the (1) first 25% of subjects enrolled complete the Week 4 visit (Visit 5); (2) first 50% of subjects enrolled complete the Week 4 visit (Visit 5); and (3) first 75% of subjects enrolled complete the Week 4 visit (Visit 5).

The study consists of a Screening Period (1 to 5 weeks), a single-blind Run-in Period (2 weeks), a randomized, double-blind Treatment Period (12 weeks), and a Safety Follow-up telephone call (2 weeks). The Safety Follow-up telephone call will occur 14 days (with a window of \pm 7 days) after the subject's last dose of study drug (ie, at Week 14 for subjects who complete the Week 12 Visit, or 2 weeks after the last dose of study drug for randomized subjects who discontinue treatment early) (see Schedule of Assessments, [Section 1.3](#)). Additionally, Unscheduled Visits may be arranged for subjects with study-related safety concerns as needed.

Approximately 200 subjects will be enrolled at approximately 40 sites in the US to achieve approximately 90 evaluable IBS-D subjects (45 per treatment group). Enrollment will be competitive. The sample size justification is provided in [Section 9.2](#).

4.1.1. Clinical Hypotheses

The primary objective will be to estimate the treatment effect of vibegron relative to placebo with respect to improvement in IBS-related abdominal pain in IBS-D subjects. There is no formal statistical hypothesis. Nominal p-values from comparisons to placebo may be provided for descriptive purposes.

4.2. Scientific Rationale for Study Design

A single-blind, placebo Run-in Period will be used to assess placebo response and to ensure that subjects have adequate experience with dosing compliance and completing the diaries. The double-blind Treatment Period will include a placebo arm to accurately demonstrate and measure

the efficacy of vibegron. Subjects with IBS-D or IBS-M were chosen as the study population because the abdominal pain due to colonic contractions in these subjects is an unmet medical need that may be addressed by vibegron's ability to relax smooth muscle contractions, as demonstrated in the overactive bladder population. The study population is limited to women because data from the Phase 2 clinical study of the β_3 -AR agonist solabegron have shown improvement in IBS pain among women [Kelleher, 2008].

4.3. Justification for Dose

This study is a proof-of-concept study that will evaluate the effect of vibegron in subjects with IBS-D or IBS-M. The dose of vibegron for this study (75 mg once daily) is the same dose that was evaluated in the recent Phase 3 program for subjects with overactive bladder. The evidence to support this dose comes from the following data:

- Several Phase 2 and Phase 3 clinical studies with vibegron at doses up to 100 mg (including 75 mg) have demonstrated that it is generally safe, well tolerated, and efficacious in subjects with overactive bladder over 52 weeks of treatment:
 - Vibegron 75 mg (2 Phase 3 studies): Studies 3003 and 3004
 - Vibegron 50 mg and 100 mg (2 Phase 3 studies and 1 Phase 2b study): Studies 301, 302, and 008
- Study 008 demonstrated dose-dependent significant efficacy over placebo across multiple clinical endpoints in overactive bladder, with the maximal effect generally estimated at doses between 50 and 100 mg
- Compared with placebo, no clinically relevant differences in heart rate or blood pressure were observed for vibegron (50 and 100 mg once daily) in the overactive bladder population
- Vibegron 75 mg administered once daily is expected to capture approximately 90% of the efficacy of 100 mg daily; the mean trough concentration for vibegron 75 mg at steady-state is 40 ng/mL, which is several fold above the β_3 half-maximal effective concentration of 1.7 nM (0.76 ng/mL)

The dose of vibegron used in this IBS study (75 mg once daily) is expected to have a similar safety profile to that observed with the same dose in the overactive bladder population.

